**Table 9. Monitoring rule for safety.** 

Stop if safety events are seen	2	3	4	5
in N patients	2	3-6	7-9	10-12

The operating characteristics of the stopping rule shows the percent of the time that the monitoring rule would pause the study under different hypothetical risks of toxicity, along with the average sample size (based on 5000 simulations).

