# 1.0 SCHEMA

Total Number of Patients: 15

Olaparib is taken 300 mg BID orally

Ascorbate is given 1 g/kg, 2 times per week intravenously (first three doses [over 1.5 weeks]: titrate 0.25 g/kg, 0.5 g/kg, and 0.75 g/kg. Starting with cycle 1 week 2, the dose of Ascorbate will be 1 g/kg as long as this dose is tolerated)

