#### 3.0 STUDY DESIGN

This is a multi-center phase II study to evaluate the safety and clinical activity of the combination of olaparib and high-dose IV ascorbate, as second or later line of therapy, in castration resistant prostate cancer patients with no known DNA repair gene mutations (DDRm). In brief, the primary endpoint is  $PSA_{50}$  response, defined by a 50% reduction in PSA from baseline. The secondary endpoints are assessing the PSA doubling time, radiographic and PSA PFS, safety and tolerability as defined by the incidence of grade 3 to 5 toxicities, and measuring overall survival. For complete endpoint definitions, see **Sections 13.2-13.4**. The total accrual for this clinical trial will be 12 men with castration resistant prostate cancer (n=12).

Olaparib will be administered at 300 mg PO BID; ascorbate will be administered at 1 g/kg IV twice weekly at least 24 hours apart until objective disease progression or unacceptable toxicities or patient withdrawal for other reasons.

The study will consist of a screening period (within 28 days of the first dose), treatment period, and follow-up period. Dose reductions are allowed per **Section 8.2.** Enrollment will continue until 15 subjects (allows for 3 drop outs) have received at least one dose of study treatment.

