# 13.5 Sample Size/Accrual Rate

Accrual to this study is expected to be one patient per month. For this combination to be considered for further study a  $PSA_{50}$  response of 23% or more would be desirable. Our null hypothesis of 3% is based on the low  $PSA_{50}$  response rate, 3% (1 of 33), reported by Mateo et al. for this patient population. This single-stage design has a 95% chance ( $\alpha$  = 0.05) of rejecting the therapy if the true percentage of patients with some benefit from treatment is less than or equal to 3% and an 80% chance of concluding the therapy is beneficial if the true percentage is 23% or more. Twelve patients, will be assessed for 6 months and if 2 or more achieve a  $PSA_{50}$  response, the therapy will be considered for a larger study. Patients enrolled who never receive any study related therapy will be

replaced. Enrollment would be allowed to continue, up to a maximum of 15 patients, to replace those patients that drop-out early.

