**Table 10. Operating Characteristics for Safety** 

Risk of safety event	0.15	0.25	0.30	0.35	0.40	0.45	0.50
% of Time Study Stops	7.4%	26.5%	39.8%	52.3%	67.8%	78.6%	86.3%
Expected Sample Size	11.5	10.4	9.6	8.7	7.7	6.9	6.1

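### Tables 9 and 10 describe a 12-patient trial, but the plan allows 15 dosed patients; the boundary is not written out for patients 13 to 15, and the expected sample sizes do not apply to 15.

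*Combined protocol and SAP*

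**What the plan says.** **Number of patients.** The schema (Section 1.0) gives "Total Number of Patients: 15". Section 3.0 first states "The total accrual for this clinical trial will be 12 men with castration resistant prostate cancer (n=12" and then, two paragraphs later, "Enrollment will continue until 15 subjects (allows for 3 drop outs) have received at least one dose of study treatment". Section 13.5 sets the efficacy decision on 12 ("Twelve patients, will be assessed for 6 months and if 2 or more achieve a" PSA50 response) and allows enrolment to go on "up to a maximum of 15 patients, to replace those patients that drop-out early".

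**Safety rule.** Section 13.6 monitors continuously for grade 3-4 events that have not resolved to grade 2 after four weeks off drug. Enrolment is held if the posterior probability that the risk exceeds 0.30 is at least 65%, with a Beta(2,6) prior. No upper limit on the number of patients is given.

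**Tables.** Table 9 ("Stop if safety events are seen") lists 2 events in 2 patients, 3 in 3-6, 4 in 7-9 and 5 in 10-12, and ends there. Table 10 gives the percentage of trials stopped and the "Expected Sample Size" from 5000 simulations. Neither the table nor the text introducing it states the maximum number of patients simulated.

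**Who counts for safety.** Section 12.4 assesses all safety outcomes in everyone who received at least one dose of olaparib and IV ascorbic acid. It has no cap at 12 and no exception for patients replaced for efficacy.

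**The concern.** Section 3.0 counts the 15 in dosed men, so those who drop out have been exposed and can have a safety event. Drop-out may also be linked to toxicity: Section 13.7 makes patients unevaluable if they lack adequate PSA data because they stopped for toxicity, and Section 13.5 replaces early drop-outs. Toxicity can therefore itself push enrolment past 12, where Table 9 is silent.

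Two things are at stake. First, staff who work from Table 9 have no entry for patients 13 to 15 and could reasonably stop checking, carry the 5 forward, or recompute the posterior. These give different chances of stopping. Second, whoever relies on Table 10 to judge the rule sees figures for a smaller trial than the one the plan permits. Section 4.2.8 says the two agents have not previously been combined in this disease, so the rule's stated performance matters.

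**Working it through.** **Inputs.** Prior Beta(2,6), risk threshold 0.30 and posterior cut-off 0.65 (Section 13.6); boundary (Table 9); stopping percentages and expected N (Table 10); maximum of 12 or 15 (Sections 1.0, 3.0, 13.5).

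**Step 1: the prior.** Its mean is 2/(2+6) = 0.25 and its 5th and 95th percentiles are 0.053 and 0.521. This agrees with the 25%, 5% and 52% stated.

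**Step 2: the boundary.** After x events in n patients the posterior is Beta(2+x, 6+n−x). The boundary is the smallest x with P(risk > 0.30) ≥ 0.65. For whole-number parameters this probability equals P(Bin(n+7, 0.30) ≤ x+1). For n = 2 to 12 the result is exactly Table 9. Beyond 12:

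| n | posterior at 5 events | posterior at 6 events | boundary |
|---|---|---|---|
| 13 | 0.608 | 0.772 | 6 |
| 14 | 0.551 | 0.723 | 6 |
| 15 | 0.494 | 0.671 | 6 |

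**Step 3: reproduce Table 10.** The method is an exact recursion over binomial paths, checking after every patient. With a maximum of 12, the stopping percentages are within 1.3 points of Table 10 and expected N is within about 0.1. One standard error of a 5000-run percentage near 66.5% is √(0.665×0.335/5000) = 0.67 points, so 1.3 points is about two standard errors. Expected N identifies the maximum: at risk 0.15 it is 11.49 for 12 patients, 12.42 for 13, 13.34 for 14 and 14.26 for 15, and Table 10 prints 11.5.

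This can be checked by hand. If 7.4% of trials stop, as printed, then 92.6% run to the end. With 15 patients those alone contribute 0.926×15 = 13.9 to expected N, already above 11.5.

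**Step 4: the same rule with a maximum of 15** (boundary 6 for n = 13 to 15).

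| True risk | Stop %, Table 10 | Stop %, exact, max 12 | Stop %, exact, max 15 | Expected N, Table 10 | Expected N, exact, max 12 | Expected N, exact, max 15 |
|---|---|---|---|---|---|---|
| 0.15 | 7.4 | 7.6 | 7.9 | 11.5 | 11.49 | 14.26 |
| 0.25 | 26.5 | 26.9 | 29.1 | 10.4 | 10.35 | 12.54 |
| 0.30 | 39.8 | 40.0 | 43.5 | 9.6 | 9.57 | 11.36 |
| 0.35 | 52.3 | 53.6 | 58.3 | 8.7 | 8.71 | 10.08 |
| 0.40 | 67.8 | 66.5 | 71.8 | 7.7 | 7.81 | 8.80 |
| 0.45 | 78.6 | 77.5 | 82.6 | 6.9 | 6.94 | 7.59 |
| 0.50 | 86.3 | 86.1 | 90.3 | 6.1 | 6.11 | 6.51 |

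Like for like (exact against exact), the chance of stopping rises by 0.3 to 5.3 points and expected N by 0.4 to 2.8 patients.

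**Step 5: where the extra stopping falls.** A trial still open after patient 12 has at most 4 events, so it has at most 5 at patient 13 and cannot reach 6. At risk 0.40 the stopping probability is 66.5% with a maximum of 13, 68.5% with 14 and 71.8% with 15. The 5.3 points are therefore 2.0 at patient 14 and 3.3 at patient 15. A hold at patient 14 spares one enrolment, and a hold at patient 15 spares none.

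**Step 6: three ways to read Table 9 past 12, with 15 treated.**

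| Reading | Stop % at risk 0.30 | Stop % at risk 0.40 | Expected N at 0.30 |
|---|---|---|---|
| No stopping after patient 12 | 40.0 | 66.5 | 11.37 |
| Stated posterior rule (6 events) | 43.5 | 71.8 | 11.36 |
| Carry the 5 forward | 54.1 | 81.3 | 11.24 |

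All three give an expected N well above the 9.6 printed.

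**The case against.** The strongest reply is that nothing is broken. Table 9 only tabulates the rule in Section 13.6, which is continuous and open-ended, and the missing entry follows from it. Both tables are correct for 12, which is the design number in Section 13.5 and the accrual figure in one sentence of Section 3.0; 15 is a ceiling that may not be reached. Adding the boundary changes expected N by no more than about 0.02 patients compared with no stopping after patient 12. Nothing tells staff to carry the 5 forward, and doing so would stop the trial earlier, not later.

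Much of this stands. A reader might infer that the last three men, a fifth of those exposed, would be unmonitored. The documents do not support that: the posterior rule covers any number of patients, and the pause for adverse events of special interest (Section 13.6), the Safety Monitoring Committee (Section 12.3) and the individual discontinuation rules (Section 8.1) have no cap at 12. A reader might also infer that the tables contain arithmetic errors. They do not, since both reproduce for 12.

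The reply does not rescue Table 10 for the trial as permitted. Section 3.0 ends enrolment at 15 dosed subjects, and the schema agrees. If 15 are treated, the printed expected sample sizes are too low under every reading of the boundary.

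**Conclusion.** The point holds as a limited correction. The tables are right for 12 patients and do not describe the 15 that the plan permits. The clearest discrepancy is expected sample size, understated by up to 2.8 patients (11.5 printed, 14.3 at risk 0.15). The chance of stopping changes by at most 5.3 points, upward if the plan's own rule is applied, and the practical effect on enrolment is small. The unwritten boundary is a real ambiguity: at a risk of 0.30 the chance of stopping is 40.0%, 43.5% or 54.1% depending on how Table 9 is read past 12.

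The figures assume that all 15 are treated unless the rule stops the trial, and that each patient's outcome is known before the next is counted, an assumption under which Table 10 reproduces. With 13 or 14 treated, expected N lies between the two sets. If enrolment is in fact capped at 12 dosed patients, both tables stand as printed. The efficacy design on 12 patients is not affected (exact alpha 0.0486, power 0.801).

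**What to change.** 1. Section 3.0: reconcile total accrual of 12 with enrolment until 15 are dosed, and align Sections 1.0 and 13.5 with the result.
2. Table 9: if more than 12 can be treated, add the column 6 events in 13-15 patients. This writes out the existing rule and changes neither the prior nor the threshold.
3. Table 10: state the maximum number of patients in the caption and give the 15-patient figures from step 4 beside the 12-patient ones, so the table serves whichever number is reached.
4. Section 13.6: state that the count for the rule is the Section 12.4 safety population, including patients replaced for efficacy. Section 12.4 requires a dose of both agents, whereas Section 7.6.2 starts ascorbic acid on day 8 of cycle 1. A man who stops in week 1 may count as dosed under Section 3.0 but not under Section 12.4, so the wording should settle how he is handled.

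The cost is one table column, one recomputed table and a few sentences. No patients, visits or assessments are added.

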**Table 10. Operating Characteristics for Safety** 

Risk of safety event	0.15	0.25	0.30	0.35	0.40	0.45	0.50
% of Time Study Stops	7.4%	26.5%	39.8%	52.3%	67.8%	78.6%	86.3%
Expected Sample Size	11.5	10.4	9.6	8.7	7.7	6.9	6.1

## 13.7 Analysis of Primary Endpoint

The primary endpoint is based on  $PSA_{50}$  response. All patients who receive at least one dose of olaparib and IV ascorbic acid will be evaluable for the primary objective. If patients do not have adequate PSA data after the initiation of therapy due to stopping for toxicity or withdrawing consent, then they will be considered unevaluable. The  $PSA_{50}$  response will be calculated as a proportion with 90% confidence intervals.

**PSA**50 **response** will be defined as a decrease in the PSA to 50% less than the baseline PSA upon enrollment in the trial. Patients must receive at least one dose of olaparib and IV ascorbic acid to be considered evaluable. After the initial measurement showing a >50% decrease in PSA compared to baseline, a second measurement must confirm the decrease,

and the measurements must be at least 4 weeks apart.  $PSA_{50}$  response rate will be calculated as a proportion with 90% confidence intervals.

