# 4.2.6 Clinical Efficacy and Safety of Olaparib

Many trials have studied the clinical efficacy and safety of olaparib. The complete clinical experience with olaparib, including toxicology and safety pharmacology, is fully described in the current version of the olaparib Investigator's Brochure.

Small numbers of advanced prostate cancer patients were included in initial clinical studies of olaparib. In the initial phase I report on olaparib, 3 patients with prostate cancer were included. In a follow-up study of patients with germline BRCA mutations, 8 prostate cancer patients were included.

Recently, a larger cohort of prostate cancer patients treated with olaparib was published. Patients were treated with the FDA-approved dose of 400mg by mouth twice daily. In the trial, 50 patients were enrolled. Three patients discontinued olaparib due to adverse events. There were 30 adverse events of grade 3-4 level. Grade 3-4 events occurring in greater than 1 patient were anemia (20%), fatigue (12%), leukopenia (6%), neutropenia and thrombocytopenia (4%).

Of the patients in the study, 16 were identified to have a mutation in DNA repair genes (BRCA1, BRCA2, ATM, FANCA, CHEK2, PALB2, HDAC2, RAD51, MLH3, ERCC3, MRE11, or NBN). Eleven of 49 evaluable patients experienced a greater than 50% decline in PSA (a PSA $_{50}$  response). Six patients achieved a partial radiographic response by RECIST criteria. Every patient with a radiographic response also had a PSA $_{50}$  response. Of these 11 responders in the study, 10 were among the patients with the mutations in the tested DNA repair genes. One responder was among the remaining 33 without an identified mutation.

There are currently no studies published in hormone sensitive prostate cancer patients.

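### Treated patients without *adequate* PSA data (undefined) can leave the primary denominator and be replaced, so the reported PSA50 rate can only rise or stay equal, and the 2-of-12 rule is not tied to a fixed 12 patients

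*Combined protocol and SAP*

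**What the plan says.** Section 13.7 sets the primary analysis set: "All patients who receive at least one dose of olaparib and IV ascorbic acid will be evaluable for the primary objective". The next sentence makes an exception: "If patients do not have adequate PSA data after the initiation of therapy due to stopping for toxicity or withdrawing consent", they count as unevaluable. No number or timing of PSA values is given for *adequate*. Under Sections 13.2 and 13.7 a response needs a decline confirmed by a second value at least 4 weeks apart. Under Section 7.1 PSA is drawn on day 1 of each cycle.

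On numbers, Section 13.5 sets the go rule: "Twelve patients, will be assessed for 6 months and if 2 or more achieve a" PSA50 response, a larger study is considered. It then adds: "Enrollment would be allowed to continue, up to a maximum of 15 patients, to replace those patients that drop-out early". Section 3.0 gives a total accrual of 12, but also says: "Enrollment will continue until 15 subjects (allows for 3 drop outs) have received at least one dose of study treatment". So 15 is a ceiling for replacements in one section and reads as a target in the other.

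The null rate of 3% is 1 of 33 patients without an identified mutation in a published olaparib study. Of that study Section 4.2.6 says: "In the trial, 50 patients were enrolled" and "Eleven of 49 evaluable patients experienced a greater than 50% decline in PSA".

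Sections 12.4 and 13.8 restrict the safety summaries to patients who received both drugs. Section 9.5.1 collects adverse events from the first dose of study drug.

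**The concern.** A treated patient can leave the primary denominator for a reason linked to the regimen (toxicity, or withdrawal of consent) and be replaced by someone else. The trigger is missing PSA, not a poor PSA result, so the patients affected are early stoppers. Someone who stops in cycle 1 may have only the end-of-treatment PSA after baseline, and the plan does not say whether one value is enough. In an open-label single-arm study that question could be settled after the PSA values are known.

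The decision rests on two responders in 12, so one or two patients matter. Three things are at stake: the direction of the reported rate, the error rate of the go rule, and which 12 patients the rule applies to.

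A related gap concerns safety. If ascorbate starts on day 8, as Section 7.6.2 and one note in Section 7.1 say, a patient who stops olaparib in the first week appears in no adverse event summary. The schema in Section 1.0, the grid in Section 7.1 and Table 2 in Section 7.6 point to a start in week 1.

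**Working it through.** **Inputs.** From Section 13.5: null rate 3%, target rate 23%, 12 patients, go if 2 or more respond. From Section 3.0: 15 dosed, 3 drop-outs allowed. The plan gives no drop-out rate by reason. I assume d = 10% and 20%; 20% is the plan's own 3 in 15.

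**Formula.** P(X ≥ 2) = 1 − (1 − p)^n − n·p·(1 − p)^(n − 1).

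**The plan's own figures.** With n = 12, p = 0.03: 1 − 0.6938 − 0.2575 = 0.0486. With p = 0.23: 0.8009. The stated 5% and 80% reproduce, with little slack: the false-positive chance reaches 5% at a true rate of 3.05%.

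**Direction of the estimate.** Excluding k patients turns x/(n + k) into x/n, which is never lower and is equal only when x = 0 or k = 0. At the decision boundary with 3 drop-outs, 2/15 = 13.3% (exact 90% interval 2.4% to 36.3%) becomes 2/12 = 16.7% (3.0% to 43.8%).

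**Replacement, reading A: 3% is the rate among all treated, and drop-outs are non-responders.** With k replaced, the rate among the 12 kept is 0.03 × (12 + k)/12.

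| k replaced | Rate among those kept | P(2 or more of 12) |
|---|---|---|
| 1 | 3.25% | 5.6% |
| 2 | 3.50% | 6.4% |
| 3 | 3.75% | 7.2% |

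With random drop-out, at most 12 counted and a cap of 15, m = min(12, Bin(15, 1 − d)) and the rate is 0.03/(1 − d). This gives 5.8% at d = 10% and 6.6% at d = 20%.

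**Replacement, reading B: 3% is the rate among evaluable patients.** With the same m and a rate of 0.03, the chance is 4.8% and 4.4%. It cannot exceed 4.9%, because at most 12 are counted.

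**Exclusion without replacement.** The go rule is a count, so exclusion alone does not raise its error: 4.9% at either d under A; 4.0% and 3.2% under B.

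**Which reading do the documents support?** Section 4.2.6 gives 16 patients with a mutation and 33 without; 16 + 33 = 49, the evaluable number. The 3% was therefore observed in an evaluable set. That study's definition of evaluable is not given. Adding its one unevaluable patient to this group would give 1/34 = 2.9% against 1/33 = 3.0%, so the figures alone cannot separate the readings.

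**Fifteen dosed, rule set for 12.** If fewer than three drop out, 13 to 15 patients may be evaluable. Keeping the threshold at 2 gives P(X ≥ 2 | n, 0.03) = 5.6%, 6.4% and 7.3% for n = 13, 14 and 15. With all 15 evaluable, both readings give 7.3%.

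**Power if drop-outs are non-responders and not replaced, with 23% holding only among those who stay.** P(X ≥ 2 | 12, 0.207) = 74.4% at d = 10%; P(X ≥ 2 | 12, 0.184) = 67.7% at d = 20%. The plan's replacement gives 79.8% and 77.2%.

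**The case against.** The two sentences of Section 13.7 can fairly be read as a rule and its exception, not as a contradiction. That stands; the defect is that the exception turns on an undefined word.

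The plan also limits the loss of data. Section 7.4 asks investigators to try for a final evaluation, Section 7.4.2 includes PSA at end of treatment, and the Section 7.1 grid marks PSA in long-term follow-up, although Section 7.5.1 describes that as phone or chart review. These reduce missing PSA but do not say how the remaining cases are classified.

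The strongest objection concerns error rates. A reader might infer that replacing drop-outs by itself makes the go rule exceed 5%. The documents do not support that. It needs two conditions together: 3% must describe all treated patients, and drop-outs must be non-responders. If being unevaluable is unrelated to response, the evaluable rate is still 3% and nothing is inflated. The source is an evaluable set, which leans towards the reading without inflation.

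Replacement is also partly a legitimate choice in a pilot that decides only whether to consider a larger study. Forbidding it costs power. And 16.7% against 13.3% is a small gap beside either interval.

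**Conclusion.** The concern holds in a limited form. Following the plan as written gives a primary estimate that, compared with counting drop-outs as non-responders, moves in one direction only: 3.3 percentage points (16.7% − 13.3%) at two responders and the plan's own three drop-outs. Who leaves the denominator depends on a term that can be settled after the data are seen.

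Inflation through replacement is conditional: 5.6% to 7.2% on the less supported reading, at or below 4.9% on the other. The plan should state which it means. The 7.3% figure does not depend on the reading, but it assumes that all 15 are evaluable and that the threshold stays at 2.

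The safety gap is real for anyone given olaparib only. How many that could be depends on the ascorbate start day, on which the sections disagree.

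**What to change.** 1. **Section 13.7.** Define *adequate* in advance as two post-baseline PSA values at least 4 weeks apart. A decline already confirmed before stopping always counts as a response.
2. **Section 13.7.** Beside the evaluable estimate, with equal prominence, report the PSA50 rate in all treated patients (any dose of either drug) with the unevaluable counted as non-responders, and state whether the go decision holds there. Because the rule is a count, adding non-responders to a larger set can never undo a go. Make that check in the first 12 treated patients by enrolment order, where a 3% all-treated rate gives 4.9%.
3. **Sections 3.0 and 13.5.** Apply the 2-of-12 rule to the first 12 patients in the primary set by enrolment order; any others enter only a supportive estimate. State whether 3% and 23% refer to treated or evaluable patients. This removes the 7.3% route. It does not remove the 5.6% to 7.2% under reading A, which is why item 2 is needed with it.
4. **Sections 12.4 and 13.8.** Define the safety population as any dose of either study drug. Sections 1.0, 7.1, 7.6 (Table 2) and 7.6.2 must be reconciled on the ascorbate start day.

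**Cost.** Wording in five sections and one more reported estimate; no added patients, and replacement may continue. The all-treated rate will look less favourable if patients leave early.

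**An option, not a requirement.** The primary set could be the first 12 patients dosed with both drugs, with no replacement and drop-outs as non-responders. Its price is power of 74.4% or 67.7% at 10% or 20% drop-out if 23% holds only among those who stay; power remains 80.1% if 23% is meant for all treated. It would still leave out anyone who stops before the first ascorbate dose. Sections 13.2 and 13.7 set no deadline for confirming a response, so none should be added unless it is stated and costed.
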